receive a new supply of study medications if it is shipped via mail or sent via courier (see section 5.1.2). If a participant is unable to pick up or receive study medications via shipment or courier, the site should consult the study core team ([contact]) for further guidance.

- If safety laboratory evaluations, and a pregnancy test for female participants of reproductive potential, cannot be performed, the continuation of study treatment is at the discretion of the Investigator of Record (IoR). The site should inform the study core team of the decision of the IoR.

6. In section 6.2.4, Discontinuation Evaluations, the following instructions have been added to the Premature Treatment Discontinuation Evaluations subsection:

Alternate Completion of Post-Entry Evaluations

- The visit can be postponed within the extended visit window if needed to safely conduct a face-to-face clinic visit. If the participant can safely be seen in the clinic, the site should perform all the evaluations for the visit per the SOE in section 6.1, Letter of Amendment (LOA) #1, and LOA #2.
- If the visit cannot be completed with a face-to-face visit despite the extended visit window, the site must attempt to contact the participant by phone or other method available. During the remote contact for visit week 72 or week 96, the site should conduct a safety follow-up (such as inquiring about signs and symptoms) to determine if any AEs or SAEs have occurred since the last visit and the participant needs medical follow-up. Additionally, the site should complete the questionnaires and adherence assessment per section 6.3.9, section 6.3.10, and MOPS section 4. All other evaluations and stored samples that will be missing for the visits, and the reason why they are missing, must be documented in the participant's study file.

7. In Appendix I, Sample Informed Consent (SIC), the following has been added as a new subsection, before the Optional Lumbar Puncture subsection, in the section WHAT DO I HAVE TO DO IF I AM IN THIS STUDY?:

COVID-19 Pandemic Considerations

During the ongoing COVID-19 pandemic, the following adjustments may be made to your study visits:

- If there is an outbreak of COVID-19 in your community and you are unable to come to the study clinic, your study doctor or staff member will try to contact you by phone or other remote method if you have a study visit due. During this contact:
 - You will be asked about your health since your last study visit or contact.

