2.1 Study Design

This is a phase IV randomized, double-blinded, placebo-controlled study to assess the efficacy of adding Maraviroc (MVC) and Dolutegravir (DTG) to the current antiretroviral therapy (ART) of HIV-infected individuals with undetectable (<50 copies/mL) plasma HIV-1 RNA, who have mild to moderate neurocognitive impairment, with a primary outcome of improvement in neurocognitive performance.

DURATION 96 weeks

SAMPLE SIZE 186 participants

POPULATION Participants will have HIV-associated neurocognitive disorder (HAND) as defined by the Frascati criteria, plasma HIV-1 RNA <50 copies/mL within 90 days prior to entry, and no more than one plasma HIV-1 RNA ≥ 50 and <200 copies/mL in the past 6 months prior to entry with a subsequent plasma HIV-1 RNA <50 copies/mL, and on stable ART for at least 6 months prior to entry with no plans to change treatment.

STRATIFICATION Participants will be randomized in a stratified manner. Stratification variables will be CD4+ nadir (≤ 100 vs. > 100 cells/mm³), and HAND severity (asymptomatic neurocognitive impairment [ANI] vs. mild neurocognitive disorder [MND] / HIV-associated dementia [HAD]).

REGIMEN At entry participants will be randomized to one of the following:
- Arm A: Add to their existing ART: placebo for MVC and placebo for DTG
- Arm B: Add to their existing ART: DTG and placebo for MVC
- Arm C: Add to their existing ART: MVC and DTG

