2.4 Overview of Sample Size Considerations

Based on previous studies, a standard deviation (SD) of 0.7 in the 48-week change in normalized neurocognitive test score is assumed. In the sample size calculation, the null hypothesis is that there is no difference in changes of neurocognitive functioning from baseline to week 48 across the treatment arms, while the alternative hypothesis is that the change of neurocognitive functioning is at least 0.5 higher for the (MVC and DTG) arm. A Bonferroni correction has been applied to account for multiple comparisons between treatments. One interim analysis of efficacy

is planned in the middle of the study and the adjusted sample sizes assume a 15% loss to follow-up. To achieve a power of 90%, we would expect a sample size of 62 participants per group for a total 186 participants on study. See Protocol section 9.4 for further details.

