4.2 Analysis Approaches

4.2.1 Primary Analysis

The Kolmogorov-Smirnov test will be employed to check whether the primary outcome is normally distributed. If the normality assumption is not rejected, the two-sample t-test will be used for pairwise comparisons between any two arms. Otherwise, the nonparametric analogue of the two-sample t-test (ie, Wilcoxon rank-sum test) will be used as an alternative. The test will be stratified by CD4+ nadir (≤ 100 vs. > 100 cells/mm³) and HAND severity (ANI vs. MND/HAD). All pairwise comparisons will be conducted among the three study arms.

Treatment comparisons will be summarized by sex and by race. Treatment interactions with sex and race will be tested as required by NIH using multiple variable regression analyses. Subgroup analyses will be performed for the primary outcome in each participating country. In presence of significantly different results by country, the changes of neurocognitive functioning will be compared by adjusting for country effects **by Van Elteren tests**.

Sensitivity analyses will be conducted under different assumptions (e.g., impute missing z-scores of a test at week 48 by the smallest/largest/median of observed values in the same treatment arm) to assess the impact and informativeness of missing data. A per-protocol analysis which will restrict the analysis to participants who adhere perfectly to the instructions in the study protocol will be performed. **In addition, a sensitivity analysis of the effect of the Trails B score imputation (see Section 6 Appendix) will be reviewed by setting imputed scores to incomplete and then re-evaluating the primary outcome.**

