4.2.2 Secondary Analyses

1. Treatment related AEs: Time to discontinuation of medication due to AEs will be compared by treatment arm using the Kaplan-Meier approach and log-rank test; Proportion of participants with Grade 3 or Grade 4 clinical AEs or laboratory abnormalities will be compared by treatment arm, using Fisher's exact tests.
2. Change in neurocognitive scores: See 4.2.1 Primary Analysis above.
3. Change in functional status: Pairwise comparisons will be performed among three treatment arms using the Wilcoxon rank-sum test.
4. Change in biomarkers: The Wilcoxon signed-rank test will be used to assess the changes from baseline to week 48 in specified biomarkers. Comparisons of changes in these biomarkers between any two treatment arms will be conducted through Wilcoxon rank-sum test.
5. Plasma HIV-1 RNA: For each treatment arm, the proportion of participants with ≥ 50 copies/mL and associated 95% CI will be provided in a table and plotted over time; Two-sided 95% CIs will also be provided for the difference between arms.
6. Changes in CD4+ cell counts: Average CD4+ counts and their associated 95% CIs will be provided and plotted over time for each treatment arm; changes in CD4+ counts from baseline to weeks 24, 48, and 96 will be compared pairwise among treatment arms through Wilcoxon rank-sum test.
7. Changes in CD8+ cell counts: Average CD8+ counts and their associated 95% CIs will be provided in a table and plotted over time for each treatment arm; changes in CD8+ counts from baseline to weeks 24, 48, and 96 will be compared pairwise among treatment arms through Wilcoxon rank-sum test.

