- Grooved Pegboard did not use a cut-off time during testing. For analysis, all scores >300 are set to 300 for calculating the T score.

Stroop (Commali version)

Norm source: Mitrushina M, Boone KB, Razani J, D'Elia L. (2005). Handbook of normative data for neuropsychological assessment. 2nd ed. New York: Oxford University Press.

- Tables A6.7.-A6.10., pages 666-668 in Mitrushina manual.
- Note- the tables were originally published by Demick and Harkins, 1997.
- Raw scores were converted to z-scores.

WAIS-III Symbol Search and Digit Symbol

Norm source: Weschler, D. (1997). Wechsler Adult Intelligence Scale, Third Edition.

- Scaled scores were defined using the manual look-up table.
- Scaled scores were converted into T scores.
- T scores were then converted to z-scores.

Hopkins Verbal Learning Test-Revised

Norm source: Brandt, J., & Benedict, R. H. B. (2001). Hopkins Verbal Learning Test – Revised. Administration manual. Lutz, FL: Psychological Assessment Resources.

- Raw scores were converted into T scores based on the manual look-up tables.
- T scores were then converted to z-scores.
- Raw scores below the range of T scores in the look-up tables were converted to z-scores using the mean and SD for the reference group as provided at the bottom of each look-up table in the manual.

Wide Range Achievement Test-4 (Green form)

Norm source: Wilkinson, G. S., & Robertson, G. J. (2006). Wide Range Achievement Test: Fourth Edition. Lutz, FL: Psychological Assessment Resources.

- Raw scores were converted into standard scores using the look-up table.
- Standard scores were then converted into z-scores.

Word Accentuation Test

Norm source: Gomar, J. J., Ortiz-Gil, J., McKenna, P. J., Salvador, R., Sans-Sansa, B., Sarró, S., Guerrero, A., & Pomarol-Clotet, E. (2011). Validation of the Word Accentuation Test (TAP) as a means of estimating premorbid IQ in Spanish speakers. *Schizophrenia research*, 128(1-3), 175–176.

- Raw scores were converted into standard scores.
- Standard scores were then converted into z-scores.

International Sites

- Raw scores were converted into z-scores using neurocognitive normative comparison test data from ACTG A5271.

7 Appendix: IADL Scoring

IADL scoring uses the following questions from NRQ0004, and scores them according to a binary scoring system using the 'NOW' response. The IADL score is the sum of the scores as defined below:

1. Housekeeping

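### Functional status, biomarker, CD4+ and CD8+ changes are compared without the randomization strata: valid, but power is lost if the strata predict change

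*SAP*

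**What the plan says.** SAP 2.1 sets up stratified randomization: "Stratification variables will be CD4+ nadir" (at most 100 versus above 100 cells/mm³) and HAND severity (ANI versus MND/HAD), which makes four strata. SAP 4.2.1 uses the same factors for the primary comparison: "The test will be stratified by CD4+ nadir" and HAND severity. SAP 4.2.2 item 2 carries that over to the secondary neurocognitive scores: "Change in neurocognitive scores: See 4.2.1 Primary Analysis above".

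The other continuous or ordinal outcomes in 4.2.2 are treated differently:

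- Item 3: "Change in functional status: Pairwise comparisons will be performed among three treatment arms using the Wilcoxon rank-sum test".
- Item 4 (blood and CSF biomarkers): between-arm comparison by rank-sum test, no strata named.
- Items 6 and 7: CD4+ and CD8+ changes "will be compared pairwise among treatment arms through Wilcoxon rank-sum test", no strata named.

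SAP 4.1 has no general rule extending the strata to these items, and no reason for the difference is stated.

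**The concern.** When randomization is stratified, the arms are balanced on the strata by design. Any part of the outcome's variance that lies between strata then no longer contributes to the chance difference between arms. An unstratified rank-sum test still counts that part in its null variance. The test stays valid, but it rejects less often than its nominal level and gives up power. A stratified test recovers it.

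A link between strata and outcome is plausible for two of these endpoints. HAND severity separates asymptomatic from symptomatic impairment, and the IADL score is a sum of eight binary items, so a participant at the maximum cannot improve. CD4+ nadir is a stratum, and item 6 compares CD4+ change. At stake is some power for Secondary Objective 3 (functional status) and for the marker and cell-count comparisons.

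**Working it through.** **1. Evaluable number per arm.** From SAP 2.4: SD 0.7, difference 0.5, power 90%, Bonferroni correction, and "the adjusted sample sizes assume a 15% loss to follow-up". Section 2.4 states neither the number of comparisons nor sidedness; I take three two-sided tests at 0.05/3.

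n = 2 (2.394 + 1.282)² × (0.7/0.5)² = 52.96 evaluable per arm; 52.96/0.85 = 62.3. The plan states 62, so its figure reproduces. Going the other way, 62 × 0.85 = 52.7, so 53 per arm is used below.

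**2. How conservative the unstratified test becomes.** Let R² be the share of variance in change explained by the strata. With arms balanced within strata, the statistic has null variance of about 1 − R² instead of 1. The rejection rate at nominal two-sided 0.05 is then about 2Φ(−1.96/√(1 − R²)):

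- R² = 0.10: 1.96/0.949 = 2.066, giving 0.039
- R² = 0.20: 1.96/0.894 = 2.191, giving 0.028
- R² = 0.30: 1.96/0.837 = 2.343, giving 0.019

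Simulation agrees: 0.051 at R² = 0, 0.041 at 0.10 and 0.022 at 0.30.

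**3. Power, continuous change score.** Assumed: normal change, 53 per arm, four equal strata with near-balanced allocation, the two factors contributing equally to R², two-sided 0.05 (no alpha is stated for secondary outcomes), 20,000 simulated trials per cell. Rank statistics use tie-corrected variances; Van Elteren weights are 1/(N_h + 1), where N_h is the stratum size. Effects are in units of the total SD of change.

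| R² | 0.4 SD: unstratified | 0.4 SD: Van Elteren | 0.55 SD: unstratified | 0.55 SD: Van Elteren |
|---|---|---|---|---|
| 0 | 0.513 | 0.501 | 0.785 | 0.773 |
| 0.05 | 0.513 | 0.523 | 0.783 | 0.789 |
| 0.10 | 0.510 | 0.542 | 0.794 | 0.811 |
| 0.20 | 0.503 | 0.592 | 0.808 | 0.855 |
| 0.30 | 0.505 | 0.644 | 0.819 | 0.900 |

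Unequal strata (10/30/15/45%) give the same pattern at 0.4 SD: 0.510 versus 0.498 at R² = 0, and 0.507 versus 0.647 at R² = 0.30.

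**4. Power, IADL sum.** Assumed throughout: ANI participants start at the maximum of 8 and can only lose items (change −Binomial(2, p); p is 0.1 in both arms, 0.1 control versus 0.05 treated, or 0.02 in both arms). MND/HAD participants start at Binomial(8, 0.6), lose a held item with probability 0.1, and gain a missing item with probability 0.05, 0.15 or 0.25 in control and 0.20 higher on treatment. The ANI share is 0.3, 0.5 or 0.7. That makes 3 × 3 × 3 = 27 scenarios, each with 10,000 trials.

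The net drift of MND/HAD controls is 3.2 × gain − 4.8 × 0.1 items, that is −0.32, 0 or +0.32. Van Elteren minus unstratified power, in points:

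| Control drift (items) | Range of difference |
|---|---|
| −0.32 | −4.0 to 0.0 |
| 0 | +0.7 to +7.0 |
| +0.32 | +3.4 to +13.2 |

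The median over all 27 is +3.1. The unstratified test is ahead by more than 1 point in 7 scenarios, all with declining controls. Null rejection is 0.036–0.052 unstratified and 0.044–0.055 for Van Elteren. At alpha 0.0167 the difference runs from −2.7 to +13.1, median +2.6.

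**5. Small samples.** The protocol's letter of amendment places new consent text "before the Optional Lumbar Puncture subsection", so CSF may come from a subset. With an assumed 10 per arm and a 0.9 SD effect, power is 0.458 versus 0.393 at R² = 0, 0.455 versus 0.428 at 0.10, and 0.447 versus 0.523 at 0.30. Four strata are then too thin unless the association is strong.

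**The case against.** Both tests are valid, and neither is better everywhere. If the strata carry no information the planned test is about 1 point ahead. At R² = 0.05 the stratified test gains only about 1 point. These are change scores, so stable baseline differences between strata are already subtracted, and nothing in the documents points to an R² of 0.20 or 0.30. The IADL figures rest wholly on assumed inputs, and even their sign depends on how untreated MND/HAD participants drift.

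The SAP can also be read as consistent: it stratifies the neurocognitive scores and names strata for no other between-arm comparison, including the log-rank and Fisher tests in 4.2.2 and the virologic and BDI tests in 4.2.3. Finally, protocol section 9 and the Analysis Implementation Plan are not among the supplied documents and could hold a rule or a rationale.

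All of this stands as a limit on the size of the point. It does not remove it. The SAP names strata where it wants them, so a programmer following items 3, 4, 6 and 7 would run unstratified tests. For a continuous outcome the trade is lopsided: about 1 point at risk against 3 to 14 points at R² of 0.10 to 0.30 (0.4 SD effect). For IADL the balance is less one-sided, but most of the scenarios favour stratifying.

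**Conclusion.** The point holds and is minor. Items 3, 4, 6 and 7 of SAP 4.2.2 omit the randomization strata without explanation. The result is conservatism and possible loss of power, not bias or false positives, and the primary analysis is untouched.

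The size depends on an association that the documents do not give. For continuous changes the loss is about 2 to 3 points at R² = 0.10, 5 to 9 at 0.20 and 8 to 14 at 0.30, across the two assumed effect sizes; below R² of about 0.05 there is little in it either way. For IADL the assumed scenarios run from a 4.0-point advantage for the planned test to a 13.2-point advantage for the stratified one. Confidence is medium, because R², the effect sizes, alpha and the IADL behaviour are all assumed.

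**What to change.** In SAP 4.2.2 items 3, 6 and 7, and for the blood markers in item 4, state that pairwise comparisons use the Van Elteren test stratified by CD4+ nadir and HAND severity. Add a descriptive summary of IADL change within each HAND stratum. For CSF markers, keep the unstratified test or collapse the strata. If the unstratified test is kept for the other outcomes, say why.

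The cost is SAP wording and one stratified rank test, which 4.2.1 already names for country effects. Under the assumed inputs the downside is about 1 point of power for a continuous outcome if the strata are uninformative, and up to 4 points for IADL if MND/HAD controls decline.

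A separate detail can be settled in the same edit. SAP section 7 says "The IADL score is the sum of the scores as defined below", yet telephone response 8e is scored N/A with no rule for how it enters the sum. One option is to leave that item out of both visits for the participant concerned, so that a change in telephone access does not count as functional change.

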4.2.3 Other Analyses

1. Changes in virologic measures: Wilcoxon rank-sum test will be used to compare Arm A and Arm B to assess the effect of DTG intensification on virologic changes.
2. **BDI Analyses: Change will be compared pairwise among the three treatment arms using the Wilcoxon rank-sum test. Percent of participants with BDI score >13 vs ≤ 13 will be compared by arm using the Chi-Square test.**

3. Correlation Analyses: Spearman correlations and scatterplots will be used to assess associations between:
 - a. Peripheral blood and CSF biomarkers and neuropsychological performance at weeks 0, 24, 48, 72, 96 (weeks 0 and 48 only for CSF biomarkers).
 - b. Changes in blood immunologic markers and changes in neurocognitive performance from baseline to week 48.
 - c. Changes in blood biomarkers from baseline to week 48.
 - d. **DTG and MVC PK and neuropsychological performance at weeks 24 and 48.**

5 Report Contents

Detailed descriptions of the content for each of the following sections are given in the AIP.

- CONSORT Diagram
- Accrual – summarize enrollment
- Baseline characteristics
 - Age
 - Sex
 - Race
 - IV drug use
 - Country
 - Education
 - Primary Language
 - HAND diagnosis
 - Nadir CD4 count
 - CD4 count
 - Log10 HIV-1 RNA
 - Neurocognitive test score
- Study status
- Treatment status
 - Premature study treatment discontinuation reasons
- Study conduct
 - Missed visits
- Safety Summary
- Analysis of primary outcome measures
 - Subgroup analyses
 - Sensitivity analyses
- Analysis of secondary outcome measures
- Analysis of other outcome measures

6 Appendix: Neuropsychological Norms For ACTG A5324

Domestic Sites

Trail Making A & B, Grooved Pegboard, Semantic and Letter Fluency

Norm source: Heaton RK, Miller SW, Taylor MJ, Grant I. (2004). Revised comprehensive norms for an expanded Halstead-Reitan battery: demographically adjusted neuropsychological norms for African American and Caucasian adults. Lutz, FL: American Psychological Assessment Resource, Inc.

- T scores were generated using the manual look-up tables.
- T scores were then converted to z-scores.
- Norms for African Americans were used for Hispanic and Native American participants.
- Trails B used a cut-off time of 240 seconds instead of the expected time out score of 300 seconds. Scores ≥ 240 are imputed to 300 for calculating the T score (unless a comment from the site provides an exact time).
- Grooved Pegboard did not use a cut-off time during testing. For analysis, all scores >300 are set to 300 for calculating the T score.

Stroop (Commali version)

Norm source: Mitrushina M, Boone KB, Razani J, D'Elia L. (2005). Handbook of normative data for neuropsychological assessment. 2nd ed. New York: Oxford University Press.

- Tables A6.7.-A6.10., pages 666-668 in Mitrushina manual.
- Note- the tables were originally published by Demick and Harkins, 1997.
- Raw scores were converted to z-scores.

WAIS-III Symbol Search and Digit Symbol

Norm source: Weschler, D. (1997). Wechsler Adult Intelligence Scale, Third Edition.

- Scaled scores were defined using the manual look-up table.
- Scaled scores were converted into T scores.
- T scores were then converted to z-scores.

Hopkins Verbal Learning Test-Revised

Norm source: Brandt, J., & Benedict, R. H. B. (2001). Hopkins Verbal Learning Test – Revised. Administration manual. Lutz, FL: Psychological Assessment Resources.

- Raw scores were converted into T scores based on the manual look-up tables.
- T scores were then converted to z-scores.
- Raw scores below the range of T scores in the look-up tables were converted to z-scores using the mean and SD for the reference group as provided at the bottom of each look-up table in the manual.

Wide Range Achievement Test-4 (Green form)

Norm source: Wilkinson, G. S., & Robertson, G. J. (2006). Wide Range Achievement Test: Fourth Edition. Lutz, FL: Psychological Assessment Resources.

- Raw scores were converted into standard scores using the look-up table.
- Standard scores were then converted into z-scores.

Word Accentuation Test

Norm source: Gomar, J. J., Ortiz-Gil, J., McKenna, P. J., Salvador, R., Sans-Sansa, B., Sarró, S., Guerrero, A., & Pomarol-Clotet, E. (2011). Validation of the Word Accentuation Test (TAP) as a means of estimating premorbid IQ in Spanish speakers. *Schizophrenia research*, 128(1-3), 175–176.

- Raw scores were converted into standard scores.
- Standard scores were then converted into z-scores.

International Sites

- Raw scores were converted into z-scores using neurocognitive normative comparison test data from ACTG A5271.

7 Appendix: IADL Scoring

IADL scoring uses the following questions from NRQ0004, and scores them according to a binary scoring system using the 'NOW' response. The IADL score is the sum of the scores as defined below:

1. Housekeeping

- a. I maintain my house/apartment by myself or only need occasional help for larger jobs.....1
- b. I only perform light daily tasks (wash dishes, make bed).....0
- c. I perform some light tasks, but have difficulty keeping my place clean.0
- d. I need help with all housekeeping tasks.....0
- e. I am fully able to do housekeeping, but choose not to do so.....1

2. Managing Monies

- a. I manage all of my monies by myself.....1
- b. I manage routine small purchases, but need help with other checking and balancing accounts.....0
- c. I am not able to handle money accurately.....0
- d. I am able to handle my own monies, but someone else does them for me.....1

4. Cooking

- a. I plan, prepare and serve many of my own meals.....1
- b. I prepare meals if someone else provides me with the right ingredients.....0
- c. I heat and serve meals provided by others.....0
- d. I need to have meals prepared and served to me.....0
- e. I am able to plan, prepare, and serve my own meals but someone else does it for me.....1

7. Transportation

- a. I drive my own car or take public transportation on my own (if you do not own a car).....1
- b. I arrange my own travel using taxis, but do not drive or use public transportation.....0
- c. I can travel on public transportation or use taxis if I am assisted by another.....0
- d. I am entirely dependent on others to take me where I need to go.....0

8. Using the telephone

- a. I handle using the telephone without difficulty (looking up and dialing new numbers, etc.).....1
- b. I only dial a few well-known numbers.....0
- c. I answer the telephone, but do not dial.....0
- d. I do not use the telephone at all.....0
- e. I do not have access to a telephone.....N/A

12. Shopping (e.g., clothes, other non-food goods)

- a. I take care of all of my shopping needs.....1
- b. I only make small purchases.....0
- c. I need someone to go with me on any shopping trip.....0
- d. I am unable to shop.....0

e. I am able to shop, but choose to have someone else do my shopping for me.....1

13. Laundry

a. I do all of my own laundry.....1
b. I need occasional help in doing the laundry.....0
c. I launder only small items (e.g., rinse socks, stockings, etc.).....0
d. All laundry must be done by others.....0
e. I am able to do my own laundry, but choose to have others do it for me.....1

14. Taking/keeping track of medication

a. I can take my medication without help.....1
b. I take medications that are prepared by someone else.....0
c. I am unable to track my own medications.....0
d. I am able to take care of my own medications, but choose to have someone else do it for me.....1

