1.2 Version History

Major changes to the previous version are noted in **bold face** throughout the document.

The SAP has been updated prior to final analysis and based on discussions with the study team.

Version	Changes Made	Date Finalized
1	Original Version	05/19/2017
2	Update for Protocol v2.0, LOA #3	03/28/2019
3	Updated for final analysis and LOA #4: Updated the viremia outcome to exploratory, added a BDI-related exploratory outcome, updated the functional status analysis, added missing data handling, and added appendices describing neurocognitive test scoring procedures and IADL scoring procedures; clarifications throughout	02/12/2021

2 Study Overview

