3.3 Other Outcome Measures

1. Changes from baseline to week 48: residual viremia, cell-associated HIV-1 RNA/DNA/2-LTR circles and SCA, T-cell and monocyte activation.
 - Aligns with Secondary Objective 10
 - Looking specifically at the comparison between DTG only arm and placebo arm to determine the effect of DTG intensification on these factors
 - **NOTE: This outcome measure was listed as secondary in the protocol but the intention was as an exploratory outcome due to lack of funding for testing, specifically for T-cell and monocyte activation**
2. Beck Depression Inventory (BDI) evaluations
 - **New outcome measure**
 - **Change in BDI score (evaluated as the sum of the 21 items) from baseline to weeks 24, 48, 72, and 96**
 - **Change from baseline in BDI score by subscales:**
 - Cognitive (items 1, 2, 3, 5, 6, 7, 8, 9, and 14)
 - Affective (items 4, 10, 12, and 13)
 - Somatic (items 11, 15, 16, 17, 18, 19, 20, and 21)
 - **Percent of participants with a BDI score \leq 13 vs. $>$ 13 at weeks 24, 48, 72, and 96**
3. **Associations of neuropsychological performance with plasma and CSF biomarkers and at weeks 0, 24, 48, 72, and 96 (0 and 48 only for CSF biomarkers); and with DTG and MVC PK at weeks 24 and 48.**
 - **Aligns with Secondary Objectives 5, 8, 9**

4 Statistical Principles

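### The exploratory comparison of BDI >13 versus ≤13 leaves out baseline BDI, so it mixes persistent, new and resolved cases and gives up some power

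*SAP*

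**What the plan says.** SAP section 3.3, item 2, defines two kinds of BDI outcome. The first uses baseline: "Change in BDI score (evaluated as the sum of the 21 items) from baseline to weeks 24, 48, 72, and 96", with three subscales treated the same way. The second is the percentage of participants at or below versus above "13 at weeks 24, 48, 72, and 96". Baseline is not among its time points.

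Section 4.2.3, item 2, assigns the tests. For the score: "BDI Analyses: Change will be compared pairwise among the three treatment arms using the Wilcoxon rank-sum test". For the split: "Percent of participants with BDI score >13 vs ≤ 13 will be compared by arm using the Chi-Square test". The second sentence has no baseline term and no strata, and it does not say whether the comparison is pairwise or across all three arms at once. No count of participants who cross the cut-off in either direction is described.

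Three other places bear on this:
- The version history in section 1.2 says that version 3 "added a BDI-related exploratory outcome".
- Section 2.1 says "Participants will be randomized in a stratified manner", with CD4+ nadir and HAND severity as the factors. BDI is not one of them.
- The baseline characteristics listed in section 5 do not include BDI. That section leaves detailed content to the Analysis Implementation Plan, which is not among the documents.

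**The concern.** The percentage above 13 at a visit is the sum of two groups: those above 13 at entry who stayed there, and those at or below 13 who crossed upward. The chi-square test sees only the sum. This has two consequences.

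- **Interpretation.** A drug effect on new cases is diluted by participants who could not become new cases. An effect on onset and an opposite effect on resolution can cancel.
- **Efficiency.** Where baseline category predicts follow-up category, an analysis that uses it has more power for an effect in one direction. It also protects against chance imbalance at entry. Baseline BDI must be available for the change outcome, so using it needs no new data.

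At stake is how much the trial can say about depression above the cut-off on the added drugs, within an exploratory outcome.

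**Working it through.** **1. Number evaluable.** Section 2.4 says "a standard deviation (SD) of 0.7 in the 48-week change in normalized neurocognitive test score is assumed", with a difference of 0.5, a Bonferroni correction and 15% loss. Taking alpha as 0.05/3 two-sided (the supplied text does not state the level), n = 2 × [0.7 × (2.394 + 1.282) / 0.5]² = 52.96 per arm, and 52.96 / 0.85 = 62.3. This reproduces the plan's figure: "To achieve a power of 90%, we would expect a sample size of 62 participants per group for a total 186 participants on study". For BDI, 62 × 0.85 = 52.7, so 53 evaluable per arm.

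**2. Assumptions.** The documents give no BDI rates. Let p be the share above 13 at entry, s the persistence among them, and a the onset rate among the rest. The follow-up rate in an arm is p·s + (1 − p)·a. Tests are two-sided at 0.05 between two arms: chi-square without continuity correction, Cochran-Mantel-Haenszel (CMH) with two baseline strata, and a test of onset alone among those ≤13 at entry. Power is by simulation, with at least 20,000 trials per case.

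**3. Only onset differs (10% vs 25%), 70% persistence in both arms.** The 15-point onset effect shrinks to (1 − p) × 15 points.

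| p | Difference seen (points) | Chi-square | CMH | Onset only |
|---|---|---|---|---|
| 10% | 13.5 | 0.39 | 0.44 | 0.50 |
| 20% | 12.0 | 0.29 | 0.34 | 0.45 |
| 30% | 10.5 | 0.22 | 0.27 | 0.41 |
| 40% | 9.0 | 0.16 | 0.19 | 0.35 |
| 50% | 7.5 | 0.12 | 0.15 | 0.30 |

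CMH gains about 0.03 to 0.06. With 50% persistence the gain is smaller: 0.31 to 0.33 at p = 20%, 0.24 to 0.25 at p = 30%, and under 0.01 at p = 50% (0.133 to 0.135).

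**4. Onset 5% vs 20%, 80% persistence in both arms, p = 30%.** Follow-up rates are 0.24 + 0.7 × 0.05 = 27.5% and 0.24 + 0.7 × 0.20 = 38%. Power is 0.22 by chi-square and 0.34 by CMH, a gain of about 0.12. Onset alone gives 0.52.

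**5. Both baseline groups move the same way, p = 40%.** Persistence is 75% vs 90% and onset 10% vs 25%. Follow-up rates are 0.4 × 0.75 + 0.6 × 0.10 = 36% and 0.4 × 0.90 + 0.6 × 0.25 = 51%. Power is 0.34 by chi-square and 0.54 by CMH, a gain of about 0.20. This case suits CMH: the odds ratio is 3 in both strata, (0.90/0.10)/(0.75/0.25) and (0.25/0.75)/(0.10/0.90). The unstratified odds ratio is (0.51/0.49)/(0.36/0.64) = 1.85.

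**6. Opposing effects, p = 30%.** Onset is 10% vs 25% and resolution 30% vs 65%. Follow-up rates are 0.3 × 0.70 + 0.7 × 0.10 = 28% and 0.3 × 0.35 + 0.7 × 0.25 = 28%. Chi-square and CMH both reject about 5% of the time. Onset alone has power of 0.40.

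**7. Validity and imbalance.** With no effect the plain chi-square rejects 4.9% to 5.4% of the time. Given an entry imbalance of 12 vs 20 of 53 above 13, with no effect, 80% persistence and 10% onset, it rejects about 14% of the time and CMH about 5%. At p = 30%, a gap of 8 or more arises in about 11% of two-arm comparisons.

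**The case against.** The strongest reply is that baseline BDI is not ignored. The sentence just before the chi-square compares change from baseline between arms, and section 3.3 applies change to the total and three subscales at four visits. A reader might infer that worsening or improvement in depression is hidden from the analysis. The documents do not support that. What is missing is narrower: crossings of the cut-off are not counted.

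A reader might also infer that the chi-square result is biased or that its error rate is wrong. It is not. Randomisation makes follow-up prevalence a fair comparison, and the overall 5% rate already allows for chance imbalance. The 14% in step 7 is conditional on one particular imbalance.

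Nor can one say that the test compares mostly pre-existing depression, or that a gain of 0.20 is typical. Both depend on rates that the documents do not give, and step 5 is a favourable case. In several cases the gain is slight and power stays low with either test.

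Finally, CMH on its own does not separate new from resolved cases, as step 6 shows. That objection stands, and it is why the tables matter more than the choice of test. The Analysis Implementation Plan may already contain such tables, which cannot be checked here.

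**Conclusion.** The point holds in a limited form. The binary BDI comparison is valid but less informative than the data allow. It pools persistent, new and resolved cases, and it leaves out a baseline measurement that the same item already uses.

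Under assumed rates and 53 evaluable per arm, the power gained by stratifying on baseline category runs from under 0.01 to about 0.20. The low end applies when few participants persist above 13 and only onset differs. The high end needs high persistence and effects in the same direction in both groups. If onset and resolution effects oppose each other, neither test shows them, and only separate summaries would.

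The outcome is exploratory, so no primary or secondary conclusion depends on it. This is a cheap improvement rather than a defect that must be corrected.

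**What to change.** In SAP section 4.2.3, item 2:
- Replace the chi-square test with pairwise CMH tests stratified by baseline BDI (>13 vs ≤13), or with logistic regression on arm and baseline BDI score. Saying that the comparisons are pairwise also settles a point that the sentence leaves open.
- Report the number and percentage with BDI >13 at baseline by arm, and add this to the baseline characteristics in section 5.
- Tabulate by arm and visit new onset among those ≤13 at entry and resolution among those >13 at entry.

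The cost is a sentence or two in the SAP and one additional table, with no new data. The small downside is that participants without a baseline BDI drop out of this test, as they already do from the change analysis.
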